#### 6.4.2.3 Modified Rodnan Skin Score (mRSS)

The modified Rodnan skin score (mRSS) calculated by summation of skin thickness in 17 different body sites using a 0–3 scale, where 0 = normal, 1 = mild thickness, 2 = moderate thickness and 3 = severe thickness. Total skin score can range from 0 (no thickening) to 51 (severe thickening in all 17 areas). Each body site needs to be scored otherwise total score should not be calculated.

#### 6.4.2.4 Baseline and Transition Dyspnea Index (BDI and TDI, respectively)

The baseline (BDI) and transition (TDI) dyspnea indices assess breathlessness in domains related to functional impairment, magnitude of task and magnitude of effort. The BDI score ranges from 0 (very severe impairment) to 4 (no impairment) for each domain and are summed to determine the BDI total score (0–12). The TDI score ranges from -3 (major deterioration) to +3 (major improvement) for each domain. The sum of all domains yields the TDI total score (-9 to +9). For both BDI and TDI, each domain needs to be answered otherwise total score should not be calculated.

#### 6.4.2.5 St. George Respiratory Questionnaire (SGRQ)

SGRQ includes three component scores: Symptoms, Activity, and Impacts and are summed to calculate the total score. Each questionnaire response has a unique empirically derived 'weight'. Symptoms component is the summed weights for the positive responses to questions 1–8 and will tolerate a

maximum of 2 missed items. Activity component is the summed weights for the positive responses to questions 11 and 15 and will tolerate a maximum of 4 missed items. Impacts component is the summed weight for the positive responses to questions 9-10, 12-14 and 16-17 and will tolerate a maximum of 6 missed items. The weight for the missed item of symptoms, activity or impacts is subtracted from the total possible weight for the corresponding component and from the total weight. The total score is calculated by summing all positive responses in the questionnaire and expressing the result as a percentage of the total weight for the questionnaire. Each component and total score range from 0 (no impairment) to 100 (maximum impairment).

#### 6.4.2.6 Scleroderma Health assessment questionnaire (SHAQ)

The SHAQ consists of the HAQ-disability index (HAQ-DI, 8 domains and an overall score) and 6 visual analogue scales assessing the burden of pain, burden of digital ulcers, Raynaud's, GI involvement, breathing, and overall disease. There are 41 total questions in HAQ-DI: 20 are 4-point Likert-scale questions, 13 questions assessing use of aids or devices, and 8 questions assessing help received from another. Twenty specific activities are assessed on a 4-point Likert-scale where 0 = without difficulty, 1 = with some difficulty, 2 = with much difficulty and 3 = unable to do. There are 3 steps to scoring the HAQ-DI:

- (1) The 20 activities are grouped into 8 functional categories with each category given a single score to the maximum value of their component activities. The score is adjusted for use of aids/help by increasing the category score from 0 or 1 to a 2 if aids/help are used for that category. If the category score is already a 2 or 3, no adjustment is made;
- (2) Sum the category scores; and
- (3) Divide the final sum by the number of categories answered to obtain the final HAQ-DI score rounded to the nearest value evenly divisible by 0.125.

A complementary scoring method ignores scores for aids and devices when computing the category scores and represents residual disability after compensatory efforts; this measure (without adjustment) will be used in our analyses. HAQ-DI requires a minimum of six categories answered; if less, the score is not calculated. The final HAQ-DI score ranges from 0 to 3. Higher HAQ-DI score indicates more disability.

Category	Variable name
Dressing and Grooming	SHAQ1DRS
	SHAQ2SHM
Arising	SHAQ3SND
	SHAQ4BED
Eating	SHAQ5MEA
	SHAQ6CUP
	SHAQ7MLK
Walking	SHAQ8WLK
	SHAQ9CLB
Hygiene	SHAQ10WAS
	SHAQ11TUB
	SHAQ12TOI
Reach	SHAQ13REA
	SHAQ14BND
Gripping and opening things	SHAQ15DOR
	SHAQ16JAR
	SHAQ17FAU

Errands and chores	SHAQ18SHP
	SHAQ19CAR
	SHAQ20VAC

The VAS scale line from the far left indicates “no pain” to the far right indicate “the most intense pain imaginable”. The measurement is between 0 to 10 cm.

#### 6.4.2.7 HRCT measures

Volumetric thoracic HRCT was done at screening and 18 months. We measured the extent of lung involvement by fibrosis (reticulations), ground glass opacity, and honeycombing on thoracic HRCT with a validated, computer-aided scoring method. High resolution CT scores are provided for quantitative extent of lung fibrosis on high resolution for the whole lung and lobe of maximum involvement and quantitative extent of total interstitial lung disease for whole lung and lobe of maximal involvement.

#### 6.4.3 Other Assessments

##### 6.4.3.1 Patient-reported outcomes measurement information system 29-item (PROMIS-29 version 2.0)

The PROMIS-29 assesses each of the seven domains with four questions with an additional pain intensity numeric rating scale (NRS) that is question 29 of the score. The seven domains include Physical Function, Anxiety, Depression, Fatigue, Sleep Disturbance, Pain Interference, and Impact on Social Roles. Each question is scored from 1-5 (with the exception of the NRS which is from 0 = no pain to 10=worst pain imaginable). The sum of each domain results in the raw score, which lies between 4 and 20. There is no total score, but each axis forms its own score. PROMIS assessments use an Item Response Theory (IRT) based score called “Expected A Posteriori” or EAP scores, which are then transformed onto a final T-score metric. This means that the scores are mapped so that the values follow a normal distribution with a population mean T-score of 50 and a standard deviation of 10. It is done by uploading the data to website: HealthMeasures Scoring Service (assessmentcenter.net). Lower scores on Physical Function and Impact on Social Roles indicate better quality of life, while higher scores on other domains indicate better quality of life.

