17.4.1 Conversion from in person to remote study visits	119
17.4.2 Components of study visits that can be carried out remotely	120
17.4.3 Components of study visits that cannot be carried out remotely.....	120
17.5 Revised site monitoring	121
18 LITERATURE REFERENCES.....	125
APPENDIX LIST	125

LIST OF ABBREVIATIONS

AE	Adverse Event
ACR	American College of Rheumatology
ADL	Activities of daily living
ALT	Alanine Aminotransferase
ANC	Absolute Neutrophil Count
ANCOVA	Analysis of Covariance
AST	Aspartate Aminotransferase
ATS	American Thoracic Society
AUC	Area under the curve
BID	Twice daily
BDI	Baseline Mahler Modified Dyspnea Index
BAL	Bronchoalveolar lavage
BUN	Blood Urea Nitrogen
CDC	Center for Disease Control
CFR	Code of Federal Regulations
CLIA	Clinical Laboratory Improvement Amendments
Cmax	Maximum concentration
CMP	Clinical monitoring plan
CMV	Cytomegalovirus
COVID-19	Coronavirus Disease 2019
Cr	Creatinine
CRF	Case Report Form
CRISS	Combined Response index in Systemic Sclerosis
CTCAE	Common Terminology Criteria for Adverse Events V4.03-2010
CYC	Cyclophosphamide
CYP	Cytochrome P450
DCC	Data Coordinating Center
DLCO	Single-Breath Diffusing Capacity of the Lung for Carbon Monoxide
DLCO-Hb-%	DLCO, adjusted for age, height, gender and hemoglobin
DMARD	Disease-modifying antirheumatic drug
DSMB	Data Safety Monitoring Board
ECG	Electrocardiogram
eCRF	Electronic Case Report Forms
ERS	European Respiratory Society
EULAR	European League Against Rheumatism
FEV1	Forced Expiratory Volume in the first second
FDA	Food and Drug Administration
FVC	Forced vital capacity
FVC-%	Forced vital capacity as a percentage of the age-, height-, gender- and race-adjusted predicted value
GERD	Gastroesophageal reflux disease
GCP	Good Clinical Practice
GOO	Ground glass opacification

GLP	Good Laboratory Practices
GMP	Good Manufacturing Practices
H&P	History and physical
HBV	Hepatitis B virus
HCV	Hepatitis C virus
Hgb	Hemoglobin
HIPAA	Health Insurance Portability and Accountability Act
HRCT	High resolution computerized tomography
HRCT-TLC	HRCT-measured total lung capacity at maximum inspiration
HRQoL	Health-related quality of life
IB	Investigator's Brochure
IFN- γ	Interferon-gamma
ILD	Interstitial lung disease
IND	Investigational New Drug Application
IPF	Idiopathic pulmonary fibrosis
IRB	Investigational Review Board
JC	Polyomavirus JC
LCQ	Leicester Cough Questionnaire
LFTs	Liver function test
MCP-1	Macrophage chemotactic protein-1
MCTM	Markov Chain Transition Matrix

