Study Duration:	Approximately 4 years total study duration, sub-divided into the following components: 
 24 month enrollment period 18-month randomized, double-blind treatment period per patient 1 month follow-up period after completion of drug therapy 6 month primary analysis period
Participant Duration:	20-22 month subject participation period made up of the following components:

	
 - screening = 1-3 months - randomized, double-blind treatment period = 18 months - final follow-up period after completion of drug therapy = 1 month
Inclusion Criteria:	
 1. Age \geq18 yrs 2. Scleroderma as determined by the 2013 ACR/EULAR classification criteria. 3. Grade \geq2 on the Magnitude of Task component of the Mahler Modified Dyspnea Index (Becomes short of breath with moderate or average tasks such as walking up a gradual hill, climbing less than three flights of stairs, or carrying a light load on the level.) 4. FVC-% of \leq85% at screening. 5. Onset of the first non-Raynaud manifestation of SSc within the prior 84 months. 6. Presence of any GGO on thoracic HRCT 7. Repeat FVC-% at the baseline visit within 10% of the FVC-% value measured at screening. If these criteria are not met, a repeat FVC-% may be obtained within 7 days and the subject may qualify for randomization if the repeat FVC-% agrees within 10% of the FVC-% obtained at screening.

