5 STUDY ENROLLMENT AND WITHDRAWAL

5.1 PARTICIPANT INCLUSION CRITERIA

In order to be eligible for randomization as a study patient, an individual must meet all of the following inclusion criteria. Notes are included, as needed, to provide additional explanation and/or background rationale for selected criteria (see bullet points). Patients will provide consent prior to the screening and screening is included as part of the consent process. Note that the screening occurs in stages in order to limit unnecessary testing:

Screening criteria that must be met prior to moving forward to HRCT imaging

- 5.1.1 Age ≥ 18 yrs
- 5.1.2 Scleroderma as determined by the 2013 ACR/EULAR classification criteria.
- 5.1.3 Grade ≥ 2 on the Magnitude of Task component of the Mahler Modified Dyspnea Index (Becomes short of breath with moderate or average tasks such as walking up a gradual hill, climbing less than three flights of stairs, or carrying a light load on the level).
- 5.1.4 FVC-% of $\leq 85\%$ at screening.
 - NOTE: Inter-test variability for FVC-% can range up to 10% and therefore some participants with an FVC-% between 80-85% at screening might exceed an FVC-% of 85% when testing is repeated at the baseline.
 - NOTE: The acceptable reproducibility of the FVC-% at baseline will be governed by inclusion criteria #7 detailed in Section 5.1.7 below.
- 5.1.5 Onset of the first non-Raynaud manifestation of SSc within the prior 84 months.
 - This criteria is based on the natural history SSc-ILD which is known to be more progressive early after the onset of scleroderma and become less active over time.

Screening HRCT imaging

- 5.1.6 Presence of any ground glass opacification (any GGO) on thoracic HRCT
 - This criteria defines a population with active and measurable parenchymal lung involvement.

Final screening criteria fulfilled at Baseline Visit, but prior to randomization

- 5.1.7 Repeat FVC-% at the baseline visit within 10% of the FVC-% value measured at screening. If

these criteria are not met, a repeat FVC-% may be obtained within 7 days and the subject may qualify for randomization if the repeat FVC-% agrees within 10% of the FVC-% obtained at screening.

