[Visit #6 (month 3), 9 (months 6), 12 (month 9), 15 (month 12), 18 (month 15), 21 (month 18)]

- j) Patient Reported Outcomes (PROs) in the form of patient responses to standardized patient questionnaires
 - SGRQ
 - [Visit #6 (month 3), 9 (month 6), 12 (month 9), 15 (month 12), 18 (month 15), 21 (month 18)]
 - SHAQ; PROMIS-29; UCLA SCTC GIT; CRISS; LCQ
 - [Visit #9 (month 6), 15 (month 12), 21 (month 18)]
- k) Complete the Mahler Transitional Dyspnea Index.
 - [Visit #6 (month 3), 9 (months 6), 12 (month 9), 15 (month 12), 18 (month 15), 21 (month 18)]
- l) An assessment of skin thickness and function scores (mRSS)
 - [Visit #6 (month 3), 9 (months 6), 12 (month 9), 15 (month 12), 18 (month 15), 21 (month 18)]
- m) Physician and Patient Global Assessments.
 - [Visit #9 (month 6), 15 (month 12), 21 (month 18)]

7.2.3.2 Additional Assessments at the 12-Month & 18 Month Visit (Visit #15 and 21).

- a) In addition to testing completed at the Regular Follow-up Visits described above, the following will take place at the 12 Month Visit:
 - Blood collection for the Biological Specimen Repository
 - The patient undergoes a complete medical history and physical examination.
- b) In addition to testing completed at the Regular Follow-up Visits described above, the following will take place at the 18 Month Visit:
 - Blood collection for the Biological Specimen Repository
 - Thoracic HRCT with Quantitative Image Analysis

7.2.3.3 Phone Follow-up Visits.

Month 0.5 (Visit #2); Month 1.5 (Visit #4); Months 7-8 (Visit #10-11); Months 10-11 (Visit #13-14); Months 13-14 (Visit #16-17); Months 16-17 (Visits 19-20)
(Visit windows ± 7 d for Visits 2 & 4; ± 10 d for all others)

- a) Focused interval history
- b) Assessment of adverse events
- c) Review of Concomitant medications
- d) Study drug reconciliation (focused review of current dose and changes since last visit, missed doses, remaining supply)

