## 12 Other Analyses

Analyses of the following outcomes will be summarized and allow for further interpretation of the study results. The m-ITT analysis set is used in the analyses.

1. The linear mixed model as described for the primary analysis of the primary endpoint is performed to compare two treatment groups on the change of the PROMIS-29 version 2.0 (in Physical Function, Anxiety, Depression, Fatigue, Sleep Disturbance, Pain Interference, Impact on Social Roles, and a single item on pain intensity) from baseline to month 18, measured by 6-month intervals. The model is adjusted by treatment, study month, interaction of treatment and study month, prior MMF therapy and baseline PROMIS-29. The model generates adjusted estimates of change from baseline in PROMIS-29 for each treatment group and month, and an F-test is used to test the hypothesis that the mean change from baseline during the treatment period differs between the two treatment groups. The model-based adjusted mean change from baseline in PROMIS-29 will be presented graphically by treatment group by study month, with 95% confidence intervals (CIs) provided at each month.
2. A frequency table and bar chart are used to show the frequency distribution of the change of QILD-WL from screening to month 18 categorized in 2% increments. The proportions of participants with better (<-2%), stable ( $\geq -2\%$  to  $\leq 2\%$ ) and worsening ( $>2\%$ ) QILD-WL in each treatment group are also presented.
3. A frequency table is used to evaluate the proportion of participants with a 3% or greater decline from baseline in FVC-% over the 18-month treatment period between the two treatment groups.
4. A frequency table is used to evaluate the proportion of participants with a 5% or greater decline from baseline in FVC-% over the 18-month treatment period between the two treatment groups.
5. Descriptive statistics are used to show the change from baseline to month 6, 12, and 18 in patient global assessment of “overall health” in the past week, overall and in each treatment group.
6. Descriptive statistics are used to show the patient transition questions of global assessment at month 6, 12, and 18 comparing patient’s (i) overall health and (ii) lung involvement to that at the baseline visit, overall and in each treatment group.

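### SAP 6.4.3.1 states the PROMIS-29 score direction backwards for at least six of the seven domains

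*SAP*

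**What the plan says.** SAP 6.4.3.1 lists seven PROMIS-29 domains: Physical Function, Anxiety, Depression, Fatigue, Sleep Disturbance, Pain Interference and Impact on Social Roles. Each has four items scored 1 to 5. Raw sums are converted by an external scoring service to T-scores with mean 50 and standard deviation 10. The section closes with the direction rule for quality of life: "Lower scores on Physical Function and Impact on Social Roles indicate better quality of life, while higher scores on other domains indicate better".

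The same paragraph describes a separate pain intensity item, "the NRS which is from 0 = no pain to 10=worst pain imaginable".

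SAP 12, item 1, fits the repeated-measures model to each domain and to pain intensity. It reports "adjusted estimates of change from baseline in PROMIS-29 for each treatment group and month" and an F-test of the treatment difference over the treatment period. SAP 5.2.3 places PROMIS-29 among the other endpoints, measured at 6-month intervals.

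SAP 5.2.3, 6.4.3.1 and 12 call the last domain Impact on Social Roles. The endpoint text reproduced in SAP 14c names it instead as an ability to take part in social roles and activities.

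**The concern.** A direction rule tells the reader which sign of a treatment difference favours which arm. Taken at face value, this one says that a patient who becomes more depressed, more anxious, more fatigued or more limited by pain has improved, and that a patient whose physical function rises has got worse.

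The SAP states no other direction for these domains, so someone writing the results has nothing in the plan to correct it. At stake is the wording of conclusions: which arm is described as doing better on quality of life.

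**Working it through.** No sample-size or power figure depends on this point, so the check is a comparison of statements.

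**Step 1. Is the instrument described consistently otherwise?** Yes. Items: 7 domains × 4 questions + 1 pain item = 29, matching the name. Raw range per domain: 4 × 1 = 4 to 4 × 5 = 20, matching the stated 4 to 20. The difficulty is confined to the direction sentence.

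**Step 2. Compare each domain name with the stated direction.** Assumption: a score measures the amount of the trait named.

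| Domain | Better, by its name | Better, by SAP 6.4.3.1 | Agree? |
|---|---|---|---|
| Physical Function | higher | lower | no |
| Anxiety | lower | higher | no |
| Depression | lower | higher | no |
| Fatigue | lower | higher | no |
| Sleep Disturbance | lower | higher | no |
| Pain Interference | lower | higher | no |
| Social roles, named as an impact | lower | lower | yes |
| Social roles, named as an ability | higher | lower | no |

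Under the name used in SAP 5.2.3, 6.4.3.1 and 12, six of seven are reversed. Under the name in SAP 14c, seven of seven are. Six is therefore a minimum under the assumption.

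**Step 3. Look for support within the SAP.** The pain item has printed anchors, and on it higher is worse. SAP 6.4.3.1 nevertheless calls more pain interference better. SAP 5.2.3 lists the pain item together with the domains. If it were counted among the 'other domains', the sentence would make the worst pain imaginable the best result.

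Elsewhere the SAP states direction in line with the trait. A higher HAQ-DI means more disability (6.4.2.6). A higher LCQ means less impact of cough, with item anchors printed to match (6.4.3.4). SAP 6.4.3.1 mentions no reverse coding that would explain the opposite convention for PROMIS-29.

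**Step 4. What does the error reach?** SAP 12 item 1 models 7 domains + 1 pain item = 8 scores. Six carry a reversed label, social roles is open, and the pain item has its own correct anchors. The direction sentence enters no formula. Tests are two-sided (SAP 8.6), and an F statistic would be the same even if every score were reflected. Estimates, intervals and p-values stand; only their verbal reading is affected.

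**The case against.** The strongest reply is that the documents print neither item anchors nor T-score direction for the seven domains, so the reversal rests on the domain names. The pain item is a raw 0 to 10 rating, described as additional to the seven T-scored domains, so it is suggestive rather than decisive. This stands as a limit. It is why all seven directions should be confirmed from the scoring output, and not only the social-roles one. It does not rescue the sentence, since nothing in the SAP suggests that a higher Depression or Pain Interference score is meant to represent less of either.

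It can also be said that no planned PROMIS-29 analysis uses the sentence. There is no responder category, testing is two-sided, and the endpoint was moved from secondary to 'other' because of the reduced sample. All of that is right, and it limits the consequence to interpretation. A reader might infer that a large set of visit-by-visit arm comparisons is wrong. SAP 12 does not support this: it specifies one F-test per score, with monthly estimates by arm shown graphically.

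SAP 14 is a record of changes, so its different name for the social-roles domain is not counted here as an error. It matters only because it leaves that domain's direction open.

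A reader might also infer a second direction error, in the dyspnea entry criterion. Protocol 5.1.3 requires grade 2 or higher "on the Magnitude of Task component of the Mahler Modified Dyspnea Index (Becomes short of breath with moderate or average tasks". SAP 6.4.2.4 describes the BDI as covering "domains related to functional impairment, magnitude of task and magnitude of effort", and scores each domain from 0 (very severe impairment) to 4 (no impairment). On that scale the number alone would admit grades 2, 3 and 4 and exclude grades 0 and 1. The documents do not establish this as an error:

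- The criterion carries its own verbal descriptor wherever it appears.
- SAP 6.4.2.4 describes outcome scoring of a BDI first given at the baseline visit (Protocol 7.1.1.4), whereas the criterion must be met earlier, before HRCT.
- The questionnaires sit in an appendix outside the available text, so the grading used at screening is not shown.
- No misclassification in the per-protocol set is shown.

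**Conclusion.** The PROMIS-29 direction statement in SAP 6.4.3.1 is wrong as written for at least six of seven domains, and for all seven if social roles is scored as an ability. That is six of the eight PROMIS-29 scores analysed. The conclusion assumes that each score measures the amount of the trait named; the pain item's anchors and the SAP's practice for its other scales support that assumption.

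No estimate, interval or p-value changes, and neither the primary endpoint nor any secondary endpoint is touched. The consequence is that a report following the SAP would name the wrong arm as better on these domains. That makes it a small error, cheap to correct and worth correcting.

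The dyspnea criterion is at most a low-priority request for clarification.

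**What to change.** In SAP 6.4.3.1, state that higher is better for Physical Function, and that lower is better for Anxiety, Depression, Fatigue, Sleep Disturbance and Pain Interference. Use one name for the social-roles domain throughout and state the direction that matches it. Confirm all seven directions against the scoring service's T-score output, and record that check before any PROMIS-29 result is interpreted. Tables and figures should carry the confirmed direction beside each domain.

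The cost is one corrected sentence, one harmonised name and one look at the scoring output. No data are collected and no model is changed.

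As an optional clarification, reconcile the dyspnea criterion (Protocol Summary, Protocol 5.1.3, SAP 6.2.1) with the scale in SAP 6.4.2.4 by stating which grading was used at screening. This review proposes no threshold.
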